6.2.1.3 Secondary analysis of primary efficacy variable

As a secondary analysis pairwise comparisons of the active neladenoson bialanate dose groups with the placebo group will be performed without controlling the family-wise error rate, by calculating the 90% confidence interval for the difference in primary efficacy variable between each active dose of neladenoson bialanate and placebo.

6.2.1.4 Sensitivity analyses of primary efficacy variable due to censoring, death, and drop outs

6.2.1.4.1 Sensitivity analysis of primary efficacy variable in PPS

The primary efficacy analysis aims at evaluating the dose-response relationship of the primary and secondary efficacy variables for all randomized patients, who have remained in the study and adhered to study treatment according to the study protocol until Week 20 (“completers and treatment adherers” analysis). Therefore, the primary analysis will be performed in the per protocol set, a subset of the FAS comprising “compliant and adherent” patients (as much as possible, defined via validity criteria). To avoid bias, the PPS will also include those “compliant and adherent” patients who are “censored” due to CV death or a hospitalization for HF preventing the assessment of the relevant efficacy endpoints 20 weeks after randomization, to take place as planned. It is expected, that these are the only patients for whom missing observations need to be considered in the primary analysis. A “worst case” approach will be used, where the missing change from baseline value will be imputed with the worst change from baseline value, which is possible given the individual baseline value observed in the respective treatment group, or 0 if the worst change in that treatment group is positive.

As a sensitivity analysis, primary analysis of primary efficacy variable on the “completers and treatment adherers” excluding the censored patients in the per-protocol analysis set will be repeated. This strategy leads to unbiased estimates only if missing values are “missing completely at random” (MCAR), i.e. the missingness – including missing data due to death – is independent of both observed and unobserved outcomes. This condition is unlikely to hold exactly but rather approximately.

Further sensitivity analyses on the PPS may be performed if the missing data patterns suggest further exploration.

6.2.1.4.2 Sensitivity analysis of primary efficacy variable in FAS

Additional efficacy analyses in the FAS will include the following:

- Primary analyses of primary efficacy variable specified in Section 6.2.1.2 will be performed in FAS without any imputation.
- Generally, it will be assumed that missing observations for the respective efficacy variables are missing at random. This implies that the behavior of the post dropout observations can be predicted from the observed variables using appropriate imputation models. Likely exceptions to the missing at random assumption are observations which are missing due to a patient's CV death or HF hospitalization prior to the visit in Week 20. These observations can be assumed to be missing not at random (MNAR), i.e., that missingness depends both on observed and unobserved outcomes and that an explicit model for the patient's statistical behavior after drop-out (or death) is required. Therefore, an analysis based on a pattern mixture framework (5) with different imputation rules depending on the reason for missingness will be used using a multiple imputation model, followed by a modification of the imputed data applying penalties:
 1. First, multiple imputation will be applied to draw sets of completed data, using an appropriate imputation model. Baseline characteristics which should be considered in the imputation model include but are not restricted to the baseline values of the respective efficacy variable, the treatment group, and sex.
 2. The imputed data will be modified by applying penalties. The penalty is chosen as the median of the worst changes from baseline across all treatment groups (or 0 if the median worst change should be positive for 6MWD/KCCQ/activity or negative for log-transformed NT-proBNP/hs-TNT).
 3. After modifying the completed data sets, the primary analysis specified in Section 6.2.1.2 will be applied to the multiply imputed datasets and the point estimate and variance of the contrast from multiple imputed dataset will be combined based on Rubin's rule (6). For more details see Appendix 9.4.
- A further sensitivity analysis will be performed where for each patient without an observation at the visit in Week 20 the missing value will be imputed according to a last observation carried forward approach, including the baseline value.

For reproducibility, the SAS seed number for creating the random numbers for the multiple imputation will be set to the study number.

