6.1 Inclusion criteria

Patients must meet all of the following inclusion criteria to be included in the study:

- 1. Men or women aged 45 years and older
- 2. Diagnosis of chronic heart failure (CHF), NYHA class II-IV (without evidence of a non-cardiac explanation for dyspnea), LVEF ≥ 45% assessed by any imaging modality (e.g. echocardiography, cardiac magnetic resonance, cine levocardiography) within the previous 6 months with no significant change in clinical status suggesting potential for deterioration in ejection fraction.

3. In the 6 months prior to run-in:

a) Requirement of treatment with a diuretic

AND

- b) Elevated natriuretic peptides, defined as *one* of:
 - o BNP \geq 75 pg/mL or NT-proBNP \geq 300 pg/mL (sinus rhythm)
 - o BNP \geq 200 pg/mL or NT-proBNP \geq 900 pg/mL (atrial fibrillation)

AND

14 FEB 2017 Version: 1.0 Page: 24 of 85

- c) At least *one* of the following:
 - o $LA \ enlargement$ (LA diameter $\geq 3.9 \ cm$, LA volume $\geq 55 \ mL$, LAVI $\geq 29 \ mL/m^2$, or LAA $\geq 20 \ cm^2$) (assessed by local imaging)
 - o LV hypertrophy (septal or posterior wall thickness ≥ 1.1 cm) (local imaging)
 - o *Elevated filling pressures* (invasive assessment) at rest (PAWP \geq 20 mmHg or LVEDP \geq 15 mmHg) or with exercise (PAWP \geq 25 mmHg) (historical records)
- 4. $6MWD \ge 100 \text{ m}$ and $\le 550 \text{ m}$ at Visit 2 (baseline)
- 5. Written informed consent signed before any study-specific procedure

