10.3.2 Statistical and analytical plans

All data will be listed and all variables will be summarized by means of descriptive statistics according to their type.

Summaries by treatment group using appropriate descriptive statistics will be provided for all study variables including demographic and baseline characteristics. Summary statistics will be presented for the original data as well as for the difference to baseline. Descriptive statistics such as mean, median, standard deviation, quantiles, minimum, and maximum will be used to summarize continuous variables. Counts and percentages will be used to summarize categorical variables. Life tables and Kaplan-Meier estimates will be used to summarize time-to-event variables. Graphical data displays may also be used to summarize the data. Confidence intervals will be provided at a 2-sided level of 90% unless otherwise stated.

For this combined proof-of-concept and dose-finding study, an overall one-sided type I error level of 5% is planned to be used. The type I error will be controlled for the primary analysis of the primary variable.

There will be no formal control of the type I error for secondary or explorative analyses of the primary variables and any analysis of other efficacy variables.

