10.3.2.2 Analysis of the primary efficacy variable

It is planned to perform a test for a dose-response signal under the assumption of a nearly monotone dose-response relationship in the dose range considered. The MCP-Mod method (84) combining multiple comparison procedures (MCP) principles with modeling techniques will be used for the primary statistical analysis of the primary efficacy variable. This method allows the flexibility of modeling for dose estimation, while preserving the robustness to model misspecification associated with MCP procedures.

14 FEB 2017 Version: 1.0 Page: 60 of 85

Assumptions

Five active doses of neladenoson bialanate will be used in this study: 5 mg, 10 mg, 20 mg, 30 mg, and 40 mg, as well as a placebo arm corresponding to a 0 mg dose.

The measurements of the primary efficacy variable are assumed to be normally distributed with the same standard deviation σ and independent between patients.

The following assumptions were made for the absolute change from baseline in 6MWD over 20 weeks:

- the expected mean effect under the placebo dose is assumed as an absolute difference from baseline of $\Lambda = 0$ m with a standard deviation of $\sigma = 80$ m
- while the maximum observable mean effect under neladenoson bialanate within the dose range considered is assumed as an absolute increase of $\Delta = 40$ m with a standard deviation of $\sigma = 80$ m.

This results in an expected maximum effect size of (40-0)/80 = 0.5.

It is assumed that the primary efficacy variable, denoted as Y, is observed for the 6 parallel groups corresponding to doses levels: (placebo =) $d_1 < d_2 < ... < d_k$, where k = 6.

For patient *j* within treatment group *i* the response can then be described by the following model:

$$Y_{ij} = f(d, \mathbf{\theta}) + \varepsilon_{ij}, \quad \varepsilon_{ij} \sim N(0, \sigma^2), \quad i = 1, ..., k, j = 1, ..., n_i,$$

where f(.) is parameterized by a vector of parameters θ and ε_{ij} is the error term.

A candidate set with M=5 different dose response shapes f(.) based on four models was chosen for the MCP-Mod method. Table 10—1 displays the response expressions for the shapes in the candidate set. Figure 10—1 shows the corresponding dose-response shapes. The model parameters were obtained through discussions with experts in the clinical team, taking prior beliefs and uncertainty into account.

Table 10—1: Dose-response shapes used in the candidate set

Model	Response as function of dose d
Linear	d

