10.4 Determination of sample size

This combined proof-of-concept and Phase IIb dose-finding study has been powered for the detection of a dose response signal in the primary efficacy variable.

The sample size for the primary efficacy variable was evaluated under the assumptions described in Section 10.3.2.2 and a type I error level = 5% with the aim to achieve at least 80% power for the one-sided primary multiple contrast test. The overall randomization ratio was assumed to be 3:1:2:2:2:2 for doses 0, 5, 10, 20, 30, and 40 mg.

Table 10—2 displays the power for the multiple contrast test in the MCP-Mod approach, used as primary analysis, for the set of specified alternatives.

Table 10—2: Power for multiple contrast test for set of different alternatives									
Sam	ple size	Pow	er for alternative	e bas	sed on respectiv	e do	se-res	ponse model (i	in %)
(oroll	Dor group a	Lincor	Ciampidal E	4	Ciamoidal E	2	_	Oundratia	Mini

Sample size			Power for alternative based on respective dose-response model (in %)						
O	verall	Per group ^a	Linear	Sigmoidal E _{max} 1	Sigmoidal E _{max} 2	\mathbf{E}_{max}	Quadratic	Minimum	
-	180	30	74.10	86.84	81.84	82.96	80.59	74.10	
	192	32	76.54	88.75	84.07	85.11	82.82	76.54	
:	204	34	78.83	90.39	86.05	87.04	84.86	78.83	
	216	36	80.84	91.81	87.80	88.72	86.61	80.84	
:	228	38	82.76	93.03	89.36	90.23	88.23	82.76	
:	240	40	84.48	94.05	90.73	91.51	89.62	84.48	
:	252	42	86.06	94.97	91.92	92.67	90.88	86.06	
:	264	44	87.45	95.72	92.96	93.65	91.96	87.45	

a Number of patients randomized to dose levels 10 mg, 20 mg, 30 mg, and 40 mg of neladenoson bialanate, for placebo sample size per group to be multiplied by 3/2, for dose level 5.0 mg sample size per group to be divided by 2.

To achieve at least 80% power for the multiple contrast test in the MCP-Mod approach under all different alternatives, a minimum of 36 patients per treatment group (54 patients for the placebo and 18 patients for the 5 mg group) is needed, resulting in an overall sample size of 216 patients.

Based on this estimation, a total of 288 patients are planned to be randomized to the 6 treatment groups:

- 72 patients are planned to be randomized to placebo (0 mg),
- 48 patients each are planned to be randomized to the dose levels 10 mg, 20 mg, 30 mg, and 40 mg of neladenoson bialanate, and
- 24 patients are planned to be randomized to the dose level 5 mg of neladenoson bialanate.

14 FEB 2017 Version: 1.0 Page: 67 of 85

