6.2.1.2 Primary analysis of primary efficacy variable

The primary efficacy analysis aims at evaluating the dose-response relationship of the primary and secondary efficacy variables for all randomized patients, who have remained in the study and adhered to study treatment according to the study protocol until Week 20 (“completers and treatment adherers” analysis). Therefore, the primary analysis will be performed in the PPS, a subset of the FAS comprising “compliant and adherent” patients (as much as possible, defined via validity criteria). To avoid bias, the PPS will also include those “compliant and adherent” patients who are “censored” due to CV death or a hospitalization for HF preventing the assessment of the relevant efficacy endpoints 20 weeks after randomization, to take place as planned. For missing post-baseline value due to CV death or study drug/study discontinuation due to HF, a worst case approach will be applied. The worst observation value (WOV) would be imputed as follows:

- 1) First, the worst change from baseline value by each treatment group will be calculated. If any of them is positive, the value would be set to 0.
- 2) Secondly the median of the worst changes from baseline value among all treatment groups would be calculated. The change from baseline value for all the missing data will be imputed with a multiplier 1.0 of this median value.
- 3) The WOV (i.e. imputed post-baseline value at week 20) will be calculated accordingly as baseline value + imputed change from baseline. If this imputed WOV for 6MWD is less than 0 (in case of either CV death or a hospitalization for HF preventing the measurement), then the WOV will be replaced with 0 and the imputed change from baseline will be modified to (- baseline value) accordingly.

All other patients with invalid/missing baseline value or missing post-baseline value due to other reasons than the above will be excluded from the PPS.

It is expected, that these are the only patients for whom missing observations need to be considered in the primary analysis. A “worst case” approach will be used, where the missing change from baseline value will be imputed with a multiple of the worst change from baseline value, which is possible given the individual baseline value observed in the respective treatment group, or 0 if the worst change in that treatment group is positive.

Statistical Analysis Plan

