6.2.2.3 Sensitivity analyses of secondary efficacy variables

Sensitivity analyses of secondary variables will be performed in the FAS the same way as for primary efficacy variable. If the baseline values of secondary endpoints are missing, then only multiple imputation will be applied for those subjects. Please see the details in Section 6.2.1.4.

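### The FAS pattern-mixture analysis penalises imputed values without the zero floor used in the primary analysis, so low-baseline patients can get a Week 20 walk below 0 m

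*SAP*

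**What the plan says.** **Primary analysis, per-protocol set (PPS; SAP 6.2.1.2).** A Week 20 value missing because of CV death or HF is replaced by baseline plus 1.0 times the median, over the six arms, of each arm's worst change. Step 3 sets a floor. If the resulting walk is below 0, "then the WOV will be replaced with 0 and the imputed change from baseline will be modified to (- baseline value) accordingly". SAP 6.2.2.2 repeats the floor for KCCQ and activity. Protocol 10.3.3 and SAP 6.2.1.2 and 6.2.1.4.1 also ask that the worst change be one the patient's own baseline allows.

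**FAS sensitivity analysis (SAP 6.2.1.4.2).** Step 1 completes the data by multiple imputation. Step 2 modifies the imputed data by penalties: "The penalty is chosen as the median of the worst changes from baseline across all treatment groups". For 6MWD, KCCQ and activity the penalty becomes 0 if that median is positive. No bound on the penalised value is given. Step 3 runs the 6.2.1.2 analysis on the modified data sets and pools the results.

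**Secondary variables (SAP 6.2.2.3).** "Sensitivity analyses of secondary variables will be performed in the FAS the same way as for primary efficacy variable".

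**Entry range (Protocol 6.1).** Baseline 6MWD may be as low as 100 m and as high as 550 m.

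**The concern.** The same patient with the same event gets a bounded score in the PPS and can get an impossible one in the FAS. The FAS analysis exists to show whether the per-protocol finding is robust. Some of any difference between the two would then come from values outside the scale. Those values fall on the weakest walkers, add variance, and could shift an arm mean if events are uneven across doses. KCCQ scores (0-100 by construction in SAP Appendix 9.3) and activity in per cent have the same problem.

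**Working it through.** **1. Planning model.** Inputs: "This results in an expected maximum effect size of (40-0)/80 = 0.5" (Protocol 10.3.2.2: placebo change 0 m, maximum effect 40 m, SD 80 m); "an overall one-sided type I error level of 5% is planned to be used" (Protocol 10.3.2); "The overall randomization ratio was assumed to be 3:1:2:2:2:2 for doses 0, 5, 10, 20, 30, and 40 mg" (Protocol 10.4). With optimal contrasts proportional to n_i(μ_i − μ̄), a multivariate t with N−6 degrees of freedom and 400,000 simulations, power at N = 216 compares with Protocol Table 10-2 as follows:

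| | Linear | Sig. Emax 1 | Sig. Emax 2 | Emax | Quadratic |
|---|---|---|---|---|---|
| Stated (%) | 80.84 | 91.81 | 87.80 | 88.72 | 86.61 |
| Recomputed (%) | 80.96 | 91.80 | 87.89 | 88.73 | 87.44 |

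All agree within 1 point, and 216/0.75 = 288. The model is read correctly.

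**2. Size of the penalty.** The SAP gives no figure, so it was simulated (20,000 trials): the minimum change in each arm, capped at 0, then the median of the six minima. The two sample sizes bracket the number of observed changes.

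| Assumption, SD 80 m | N = 216 | N = 288 |
|---|---|---|
| No effect in any arm (5-95% range) | −166 m (−197 to −138) | −175 m (−205 to −148) |
| The protocol's five shapes | −133 to −148 m | −142 to −158 m |

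The expected penalty is thus about 130-175 m at SD 80 m. With no effect it would be about 104-109 m at SD 50 m and 208-219 m at SD 100 m.

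**3. Chance of a negative walk if the penalty is added to the drawn change.** P = Φ(−(baseline + mean change + penalty)/80), with mean change 0:

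| Baseline | Penalty −133 m | −160 m | −175 m |
|---|---|---|---|
| 100 m | Φ(33/80) = 66% | Φ(60/80) = 77% | Φ(75/80) = 83% |
| 200 m | Φ(−67/80) = 20% | Φ(−40/80) = 31% | Φ(−25/80) = 38% |
| 300 m | Φ(−167/80) = 2% | Φ(−140/80) = 4% | Φ(−125/80) = 6% |

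**4. Averaged over baselines.** The documents give only the 100-550 m range, so a truncated normal with SD 100 m is assumed:

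| Assumed baseline mean | −140 m, mean change 0 | −160 to −175 m, mean change 0 | −160 to −175 m, mean change +40 m |
|---|---|---|---|
| 350 m | 5% | 7-8% | 3-4% |
| 300 m | 9% | 12-15% | 6-8% |
| 250 m | 15% | 20-23% | 11-14% |

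Before any penalty fewer than 1% of draws are negative, so the penalty is the cause.

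**5. If the penalty replaces the drawn change.** Any penalised patient whose baseline is smaller than the penalty goes below 0. For penalties of 157-175 m that is 6-9% at an assumed mean of 300 m and 12-17% at 250 m.

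**6. What the floor changes per patient.** With penalty −165 m and mean change 0, the mean imputed walk rises from 35 to about 52 m at a 200 m baseline, and from 135 to about 136.5 m at 300 m.

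**7. Effect on the test.** Event rates are not given; 3-10% is assumed, i.e. 288 × 0.03 ≈ 9 to 288 × 0.10 ≈ 29 patients. If only these are penalised (additively, linear effect to 40 m), about 1-6 patients in the whole trial fall below 0 m. Adding the floor changes the linear contrast t by about 0.01-0.02 on average (5-95% about −0.13 to +0.22). In the least favourable setting tried (mean baseline 200 m, 10% events) the average change was 0.02-0.03, and the pooled SD fell from about 92 to 89 m.

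**The case against.** **The floor may carry over.** Step 3 refers back to 6.2.1.2, where the floor is written for these same events, and the documents state the intent that the worst change be possible for the patient. This has some force as evidence of intent. But step 3 starts from data sets that are already complete, and the 6.2.1.2 floor belongs to filling in missing values. A programmer following the text would not clearly apply it.

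**The operation is not defined.** The SAP does not say whether the penalty is added to the drawn change or replaces it, or exactly which imputed patients receive it. The context points to CV death and HF hospitalisation. This stands and is part of the point. Negative values arise under either operation.

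**Stronger readings a reader might infer:**
- *That the penalty is 160-175 m.* No such figure is in the documents. Values of 166-175 m need no treatment effect; the protocol's own alternatives give 133-158 m.
- *That every low walker with an event ends below 0 m.* Under addition it is a probability: high at 100 m, roughly one in five to two in five at 200 m, and small at 300 m.
- *That the trial's conclusion is at risk.* The primary PPS analysis has the floor. The FAS is also analysed without imputation and by last observation carried forward, and neither uses a penalty.

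**The effect is small.** This stands if only event cases are penalised.

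**Conclusion.** The inconsistency is real and minor. Step 2 of the FAS analysis drops a bound that the SAP applies elsewhere to the same quantity for the same events, and the rule as written can produce impossible values.

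That conclusion needs only the text, the 100 m entry minimum, and a penalty larger than some patients' baselines. The percentages need more: SD 80 m, normal changes, an additive penalty and an assumed baseline distribution. The small effect on the test rests on assumed event rates of 3-10% and on penalising only event cases. Nothing here changes the primary analysis or its power.

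**What to change.** In SAP 6.2.1.4.2 step 2:

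1. Name the imputed patients who receive the penalty.
2. State whether it is added to the drawn change or replaces it.
3. Apply the 6.2.1.2 step 3 bound afterwards: if baseline plus change is below 0, set the Week 20 value to 0 and the change to minus baseline. Do this for 6MWD, KCCQ and activity.

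An upper cap on KCCQ is not part of this fix, because the penalty for these scores is never positive.

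The cost is two or three sentences and a line of code. There is a small downside: the penalty becomes slightly less severe for the lowest walkers, which makes this sensitivity analysis a little less conservative. That matches what the primary analysis already does.

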6.2.1.5 Additional analysis of primary efficacy variables

Adjusted primary analysis (dose-response test) of primary efficacy variables specified in Section 6.2.1.2 will be performed in PPS. Baseline values of 6MWD, age (as a continuous variable) and gender will be used as covariates.

Statistical Analysis Plan

6.2.2 Secondary efficacy variables and analyses

6.2.2.1 Secondary efficacy variables

Secondary efficacy variables across different domains are:

- AVIVO Activity intensity (weekly average; in %) reported values and absolute change from baseline at 20 weeks
- NT-proBNP (pg/mL), measured values (log transformed) and absolute / relative change from baseline at 20 weeks to assess elevated filling pressures
- High sensitivity troponin T (hs-TNT; ng/L), measured values (log transformed) and absolute / relative change from baseline at 20 weeks as a biomarker of myocardial injury
- Three scores from KCCQ, Physical Limitation, Overall Summary Score and Total Symptom Score (Appendix 9.3), derived values by visit and absolute change from baseline

